Cover page

Title: Cumulative Pregnancy Rate with Lower and Higher
Gonadotropin Dose During IVF Among Poor Responders

Trial registration: NCT05003228

Date created: Oct 4, 2021

Design: Investigator initiated prospective, randomized, multi-center, non-blinded trial to compared higher and lower gonadotropin in poor responder patients undergoing IVF-ICSI **treatment identified based on Posedion III-IV criteria**

Inclusion Criteria:

- Expected poor responder based on:
 - a) AMH: 0.3-1.2 ng/ml or AFC <5,
 - b) AMH>1.2 ng/ml or AFC \geq 5 but the retrieval of \leq 4 oocytes during previous IVF treatment.
- motile sperm with normal morphology obtained from the ejaculate of testicular biopsy
- no more than 3 previous failed IVF cycles (if the patient had 2 or more previous cycles cancelled for poor response she cannot be included)
- BMI: 18-35 kg/m²
- regular 24-35 day cycles
- intact uterine cavity
- indication for in vitro fertilisation treatment (tubal factor, male factor, low ovarian reserve, endometriosis, unexplained infertility)
- age 18-421 yrs

Exclusion Criteria:

- presence of hydrosalpinx
- positive HIV, hepatitis B, C screening tests
- planned preimplantation genetic testing of the embryos
- planned elective cryopreservation
- lack of consent
- not meeting the inclusion criteria

Treatment protocols and treatment monitoring/ steps:

Lower-dose group:

- 150 IU follitropin alpha + 75 IU highly purified human menopausal gonadotropin (hpHMG)
- 10 mcg follitropin delta + 75 IU hpHMG

Higher-dose group:

- 225 IU follitropin alpha + 150 IU hpHMG
- 15 mcg follitropin delta + 150 IU hpHMG

Treatment protocol:

- The stimulation will get started on day 2 or 3 of the spontaneous menstrual cycle, or on the 5th day after oral contraceptive pill use or after luteal estradiol pretreatment.
- During the stimulation ultrasound +/- serum hormone measurements will be used to monitor response. The first ultrasound is scheduled for day 5 or 6 of stimulation. At the time of the ultrasound blood test for serum estradiol is planned too. At the time of the last scan serum estradiol and progesterone levels will be measured.
- According to the study protocol the patient will continue with the assigned medication dose throughout her treatment. Dose increase is not allowed. If there is evidence for hyper-response [estradiol level > 4000 pmol/l on day 6 or more than 15 follicles over 10 mm any time during the stimulation] the dose can be reduced.
- As soon as two or more follicles reach >17 mm in diameter human chorionic gonadotropin (hCG) or gonadotropin-releasing hormone agonists [GnRH a] trigger injection will be used and 35-36 hours later transvaginal ultrasound guided follicle aspiration will be performed.
- The luteal phase will be supported by vaginal progesterone starting on the day after the retrieval.
- IVF or ICSI fertilization will be performed based on the semen parameters or previous fertilization records.
- The day after the retrieval the success of fertilization will be checked and the embryo(s) will be transferred 2-5 days after the retrieval. Embryo(s) will be transferred transcervically using soft transfer catheters under ultrasound guidance using the afterload technique.
- Surplus good quality embryos will be cryopreserved using vitrification. Elective cryopreservation (no transfer in the fresh cycle) will be performed if: 1) risk of ovarian hyperstimulation syndrome, 2) serum progesterone level over 1.5 ng/ml [5.5 nmol/l]

prior to the oocyte collection, 3) any complications between the retrieval and planned fresh transfer (bleeding, infection, illness).

- 12-14 days after the transfer serum human chorionic gonadotropin (HCG) measurement will determine whether implantation has occurred. If the test is positive in 2-3 weeks a vaginal ultrasound will be done to determine the size, location and number of gestational sacs. Viable pregnancies will be referred to a formal prenatal care around week 8-9 of pregnancy. Delivery and perinatal outcome data will be collected by phone call after the delivery.
- If the fresh IVF cycle is not successful but embryos have been cryopreserved then the patient will undergo a frozen embryo transfer treatment cycle either in her own cycle, or in a minimally stimulated or completely artificial cycle.

The care of the patients will not differ from the care of non-study patients in terms of potential medication dose, the number of clinic visits, retrieval and embryology procedures as well as prenatal care.

Randomization: Randomization will be performed according to a computer generated list. (www.randomizer.org) The planned sample size is 700 patients (350 in both the low- and high-dose groups).

Sample size calculation: In order to determine the sample size, the investigators calculated with a 20% pregnancy rate in a patient population that fits the inclusion-exclusion criteria. The investigators expect higher oocyte yield in the higher dose group that should result in more available embryos and therefore more frozen embryo transfers. The investigators calculate that this could increase the cumulative pregnancy rate by 50%. The investigators also believe that about 20% of the patients will drop out for various reasons. Therefore, 350 participants are needed in both arms of the study.

Statistical analysis: After the enrollment of the first 350 patients, a planned interim analysis will be performed to decide whether the planned sample size is sufficient to achieve our goal. Logistic regression analysis using a generalized, mixed linear model will be used to assess the impact of various Gn doses on pregnancy rates. Chi-square test will be used to test significance and OR will be calculated. Results are reported as intention-to-treat (ITT).

Data will be collected for the following parameters:

- Age
- Cycle day 3 follicle stimulating hormone (FSH), estradiol level
- anti-Müllerian hormone (AMH)
- antral follicle count (AFC)
- Indication for IVF: male, tubal, unexplained, endometriosis, diminished ovarian reserve
- Smoking (yes-no)
- Body mass index
- Cycle number (fresh + frozen together)
- Estradiol level on day 6
- Estradiol + progesterone level at the last scan
- Number of follicles >10 mm at the end of stimulation
- Stimulation duration
- Endometrial thickness
- Gn dose (daily, total)
- Trigger mechanism (HCG vs. GnRh agonist)
- Sperm parameters
- Oocyte number
- Mature (MII) oocyte number
- Proportion of mature oocytes (MII/ oocyte number)
- IVF vs. ICSI fertilization
- Number of fertilized (2 pronuclei (PN)) oocytes
- Fertilization rate per oocyte
- Fertilization rate per mature oocyte
- The number of good quality embryos (morphology better than score "6B2" on day 3, or score >2BB on day 5) and proportion of good morphology embryos among all embryos
- Number of transferred embryos

- Number of cryopreserved embryos
- Pregnancy rate (positive hCG)
- Clinical pregnancy rate (sac with viable embryo in it)
- Cumulative pregnancy rate (fresh + frozen embryo transfers)
- Pregnancy/ neonatal outcome

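### Non-blinded trial states no masking of the embryology laboratory, although a morphology grade decides which surplus embryos are frozen (low-priority improvement)

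*Combined protocol and SAP*

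**What the plan says.** The Design paragraph calls this an "Investigator initiated prospective, randomized, multi-center, non-blinded trial". Nothing later in the document exempts the laboratory, and no independent or central grading is described.

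The Treatment protocol section gives the freezing rule: "Surplus good quality embryos will be cryopreserved using vitrification". It then makes a later transfer depend on that step: "If the fresh IVF cycle is not successful but embryos have been cryopreserved then the patient will undergo a frozen embryo transfer treatment cycle". The data collection list defines the cumulative pregnancy rate as fresh and frozen transfers together, and this is the outcome in the trial's title. The Sample size calculation expects the higher dose to work by producing "more available embryos and therefore more frozen embryo transfers".

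Two statements limit the discretion:

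- The data collection list defines a good-quality embryo as one with morphology better than 6B2 "on day 3, or score >2BB on day 5".
- The Treatment protocol section says that care does not differ from that of non-study patients, and it includes "retrieval and embryology procedures as well as prenatal care" in that statement.

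**The concern.** The pregnancy test is objective, so the worry is not about how the outcome is read. It is about who gets a further chance at pregnancy. Freezing happens after allocation, so neither randomisation nor the intention-to-treat analysis protects this step. If graders knew the dose and leaned the same way on average across centres, leniency in the higher-dose arm would imitate the expected benefit, and leniency in the lower-dose arm would hide a real one. The step lies on the very route by which the plan expects the dose to act. Masking must be in place when embryos are graded; it cannot be added at analysis.

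**Working it through.** **1. How much judgement is left.** The freezing sentence gives no cut-off and does not refer to one. The data list uses the same term, good quality embryos, with numeric morphology thresholds. In so short a document, the natural reading is that one definition serves both places. What remains is the grading of embryos near the threshold. The statement about usual embryology procedures describes routine practice and says nothing on whether the grader knows the dose.

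**2. The plan's sample size.** The point does not depend on it, but the figures below use it. Inputs from the Sample size calculation: "the investigators calculated with a 20% pregnancy rate in a patient population", a 50% increase (read as relative, so 20% to 30%) and 20% dropout. Two-sided alpha of 0.05 and 80% power are my assumptions, because the document states neither.

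n = (1.960 + 0.842)² × (0.2 × 0.8 + 0.3 × 0.7) / 0.10² = 7.85 × 0.37 / 0.01 = 290.4, so 291 per arm. Then 291 × 1.2 = 349.2, so 350. The plan's figure is reproduced. With 20% lost, 350 × 0.8 = 280 remain.

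**3. Size of a possible shift (illustration only).** All three inputs are assumptions:

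- 5% to 10% of women in one arm have one extra borderline embryo frozen and available for transfer.
- 80% of these women are not already pregnant.
- 5% to 15% of the resulting transfers succeed, which is below the plan's own 20% rate.

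Shift = 0.8 × share affected × success:

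- low: 0.8 × 0.05 × 0.05 = 0.2 points
- middle: 0.8 × 0.075 × 0.10 = 0.6 points
- high: 0.8 × 0.10 × 0.15 = 1.2 points

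**4. Effect on the test.** I enumerated two binomials exactly and applied the pooled chi-square test without continuity correction, rejecting when |z| > 1.96. Type I error compares 20% with 20% + shift. Power compares 20% + shift in the lower-dose arm with 30% in the higher-dose arm.

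| Shift (points) | Type I, 350 per arm | Type I, 280 per arm | Power, 350 per arm | Power, 280 per arm |
|---|---|---|---|---|
| 0 | 5.0% | 5.0% | 86.6% | 78.5% |
| 0.2 | 5.0% | 5.1% | 85.2% | 76.7% |
| 0.6 | 5.4% | 5.4% | 81.9% | 72.9% |
| 1.2 | 6.8% | 6.5% | 76.3% | 66.9% |

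The bottom row needs both upper inputs together.

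**5. Whether the collected data could detect biased freezing instead.** The list records fertilised (2PN) oocytes, good-quality embryos and cryopreserved embryos, so one might compare freezing rates by arm. That comparison cannot be interpreted. Frozen embryos are what is left after fresh transfer, so an arm with more embryos freezes a larger share of them without any bias.

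To illustrate, assume Poisson 2PN counts, half of them good quality in both arms, one good embryo transferred fresh when available, and unbiased grading. With mean good-quality count g, expected frozen embryos per woman are g − 1 + e^(−g).

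- Mean 2PN 2.0 (g = 1.0): 0.368 frozen, or 18.4% of 2PN and 36.8% of good-quality embryos.
- Mean 2PN 2.5 (g = 1.25): 0.25 + 0.287 = 0.537 frozen, or 21.5% of 2PN and 42.9% of good-quality embryos.

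In simulation with 350 women per arm, an embryo-level test of frozen per 2PN would flag about 33% of such unbiased trials. With mean 2PN of 2.0 against 3.0 it would flag about 80%. More embryos in the higher-dose arm is exactly what the plan expects, so the check would present the treatment effect as bias.

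**The case against.** The strongest reply is that no error in the plan is shown. The trial openly declares itself non-blinded, the documents are merely silent on the laboratory, and the rest is hypothetical. The freezing rule is worded as mandatory, the cut-off is numeric, and the outcome is a hormone test or a scan. Harm would need leniency in one arm only, in the same direction on average across centres, with the extra embryos actually transferred. Even then, the middle case moves type I error only from 5.0% to 5.4%.

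Most of this stands, and it sets the priority. It does not remove the point, because a morphology score near a threshold still needs a grader, and nothing in the documents keeps the dose from that person.

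A reader might infer more: that embryologists know the arm, that freezing is left to free judgement, or that the result will be biased in favour of the higher dose. The documents support none of these. They do not say who sees the allocation, they give a cut-off, and they give no reason to expect leniency in either direction. Grading of surplus embryos is also not the only route to a frozen transfer, since elective cryopreservation has its own listed triggers.

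**Conclusion.** The point holds as an inexpensive improvement of low priority, not as a demonstrated flaw. It rests on three facts in the documents: the trial is non-blinded with no stated exception for the laboratory, a graded judgement decides which surplus embryos are frozen, and frozen transfers feed the title outcome and carry the expected benefit. The exposure is confined to grading near the cut-off, if the listed cut-off governs freezing as I read it. The size of any bias cannot be estimated from the documents. The illustrative shift of 0.2 to 1.2 points, against a planned difference of 10 points, runs from almost nothing to modest and depends wholly on the inputs assumed above.

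**What to change.** Add two statements to the protocol:

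1. The allocated dose is kept off laboratory request forms and records, so that embryologists who grade embryos and decide on freezing are masked as far as practicable. Patients and treating clinicians remain unmasked.
2. The morphology cut-off in the data collection list is the grade used for the freezing decision in the Treatment protocol section.

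Do not add a by-arm comparison of frozen embryos per 2PN or per good-quality embryo as a test for bias, for the reason shown above.

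The change should need only altered forms and two sentences, with no effect on sample size or patient care. That cost is an assumption, because laboratory forms and staffing are not described. Masking would be partial: oocyte numbers may hint at the arm. The protocol also does not say who decides how many embryos are transferred fresh, which determines what is surplus.

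### The progesterone limit for withholding the fresh transfer is given as two values that differ by 15%: 1.5 ng/ml is about 4.8 nmol/l, not 5.5

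*Combined protocol and SAP*

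**What the plan says.** Under Treatment protocol, the plan lists the situations in which a patient has no fresh transfer: "Elective cryopreservation (no transfer in the fresh cycle) will be performed if: 1) risk of ovarian hyperstimulation syndrome" is the first, and the second is "serum progesterone level over 1.5 ng/ml [5.5 nmol/l" (bracket closed in the source) before oocyte collection. The third is a complication between retrieval and the planned transfer.

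The same section sets when the hormone is measured: "At the time of the last scan serum estradiol and progesterone levels will be measured". The data collection list accordingly includes "Estradiol + progesterone level at the last scan", without a unit.

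The limit appears only once. The document gives no conversion factor, does not rank one unit above the other, and does not say in which unit any centre's laboratory reports. The only other steroid limit, the hyper-response criterion for reducing the dose, is in molar units alone: "estradiol level > 4000 pmol/l on day 6".

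**The concern.** A second figure in brackets after a limit in other units reads as a conversion. Here it does not convert, so the plan contains two limits while appearing to contain one.

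The line decides treatment for individual women. Someone at 1.6 ng/ml (5.09 nmol/l) exceeds the mass limit but not the molar one. What follows depends on the units in use, which the document does not state:

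- If all centres work in ng/ml, 1.5 applies everywhere and the bracket is wrong but has no effect.
- If all work in nmol/l, handling is uniform, but the limit actually applied is 1.73 ng/ml, not the stated 1.5.
- If units are mixed, which is possible in a trial described as "Investigator initiated prospective, randomized, multi-center, non-blinded trial", women with the same progesterone level could be handled differently at different centres.

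The results exposed are those of fresh transfers and the split between fresh and frozen transfers.

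**Working it through.** **Inputs.** From the protocol: the limits 1.5 ng/ml and 5.5 nmol/l (Treatment protocol), 700 planned patients (Randomization) and a 20% pregnancy rate (Sample size calculation). From outside the protocol: the formula of progesterone, C21H30O2, and standard atomic masses.

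**Molar mass.** 21 × 12.011 + 30 × 1.008 + 2 × 15.999 = 314.469 g/mol. Hence 1 ng/ml = 1000 / 314.469 = 3.180 nmol/l.

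**Attempt to reproduce the bracketed figure.**

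- 1.5 × 3.180 = 4.77 nmol/l, against 5.5 stated.
- In reverse, 5.5 / 3.180 = 1.730 ng/ml, against 1.5 stated.
- Ratio: 5.5 / 4.770 = 1.153, so the molar limit is 15.3% higher.
- Width of the disputed band: 5.50 − 4.77 = 0.73 nmol/l, or 1.50 to 1.73 ng/ml.

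**Could rounding account for it?**

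| Stated value | Range that rounds to it | Converted |
|---|---|---|
| 1.5 ng/ml | 1.45 to 1.55 ng/ml | 4.61 to 4.93 nmol/l |
| 5.5 nmol/l | 5.45 to 5.55 nmol/l | 1.71 to 1.75 ng/ml |

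The ranges do not meet. A coarser conversion factor of 3.2 gives 1.5 × 3.2 = 4.80 nmol/l, still well short of 5.5.

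**Where the figure may have come from.** The stated pair implies a factor of 5.5 / 1.5 = 3.667, and so a molar mass of 1000 / 3.667 = 272.7 g/mol. That is close to estradiol (C18H24O2, about 272.4), so the estradiol factor may have been applied to progesterone. This is an inference; the protocol does not say so, and the finding does not depend on it.

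**How many women, and how much?** The protocol does not give the share of women between 1.50 and 1.73 ng/ml, so the shares below are assumptions. The last column also assumes that the protocol's 20% rate applies to these women's fresh transfers and that every one of them would otherwise have had a fresh transfer.

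| Assumed share in band | Women (share × 700) | Change in fresh pregnancy rate per randomised woman (share × 20%) |
|---|---|---|
| 1% | 7 | 0.2 percentage points |
| 3% | 21 | 0.6 |
| 5% | 35 | 1.0 |
| 10% | 70 | 2.0 |

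The change would be alike in both arms if the share is alike.

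**The case against.** The mismatch itself is not in dispute; the case on the other side is that little follows from it.

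First, the title and the sample size reasoning centre on the cumulative rate, and the data list defines that as "Cumulative pregnancy rate (fresh + frozen embryo transfers" combined. A woman moved from a fresh to a frozen transfer still contributes, and the protocol provides for the later frozen cycle. The sample size does not depend on the limit. This stands, and it is why the effect on the cumulative rate is put as probably small.

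Second, inconsistent handling needs centres that use different units, and the document does not show this. The estradiol limit in pmol/l hints at molar units throughout, while the AMH criterion is in ng/ml, so the matter is open. This also stands: the between-centre effect is a possibility, not a demonstrated fact. But with uniform molar units the trial would still apply a limit other than its stated 1.5 ng/ml.

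Third, the assumed shares have no anchor in the protocol. The 20% is not stated to be a fresh-transfer rate, and if it is a cumulative rate it is too high for this use. Some women in the band would have had no fresh transfer anyway, through another freeze-all reason or the roughly 20% drop-out expected. Nor does the data list name a separate fresh-only rate. These points are fair. At each assumed share, the percentage-point figures are best read as upper limits, and they are not evidence that the effect is large.

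None of this makes the two figures agree or tells a centre which one to apply.

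**Conclusion.** The line is wrong as written. The two limits differ by 15.3%, and a woman between 1.50 and 1.73 ng/ml (4.77 to 5.50 nmol/l) cannot be classified from the text. Confidence in this is high; it rests only on the molar mass of progesterone.

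Confidence in the size of any consequence is low, because neither the centres' units nor the share of women in the band is given. No bias between arms is shown, since the same rule applies to both. The matter should be fixed because the rule decides whether an individual woman has a fresh transfer and the correction is nearly free, not because the main comparison is shown to be at risk.

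**What to change.** State one limit with a correct conversion: either 1.5 ng/ml [4.8 nmol/l], or 1.73 ng/ml [5.5 nmol/l] if the molar value was intended. The choice is clinical and belongs to the sponsor. All centres should then be told which limit applies.

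Optionally, if women have already been treated, count those whose progesterone at the last scan fell in the band. The level is already on the data collection list; the reporting unit is not, and would have to be obtained.

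The cost is a one-line protocol correction and a note to centres, plus the reporting unit if the count is made.

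### Significance appears to rest on an unadjusted chi-square test although baseline age, AMH and AFC are collected and a logistic model is planned; a modest amount of power is given up

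*Combined protocol and SAP*

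**What the plan says.** Two consecutive sentences under Statistical analysis matter here. The first plans a model: "Logistic regression analysis using a generalized, mixed linear model will be used to assess the impact of various Gn doses on pregnancy rates". The second says how significance is judged: "Chi-square test will be used to test significance and OR will be calculated". Results are to be reported by intention to treat. The section names no covariate or random effect, does not say which analysis is primary, and does not say whether the chi-square statistic comes from a 2x2 table or from the model.

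The list of data to be collected includes age, AMH and AFC, all known before treatment starts. It also includes variables that arise after randomisation, such as day-6 estradiol, oocyte number and embryo counts. Eligibility is partly defined by ovarian reserve (Inclusion Criteria: "AMH: 0.3-1.2 ng/ml or AFC <5", with a second route for women with higher values who had a poor previous retrieval). The Randomization paragraph describes a computer-generated list and mentions no stratification.

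The Sample size calculation starts from a 20% pregnancy rate, expects a 50% increase, and allows for loss: "The investigators also believe that about 20% of the patients will drop out for various reasons". It concludes: "Therefore, 350 participants are needed in both arms of the study".

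**The concern.** If age, AMH and AFC predict pregnancy, a test of arm adjusted for them has more power than the chi-square, with the same women and the same data. With no stratification described, nothing in the design balances these factors beyond simple chance. An unadjusted test leaves that information unused.

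A secondary point is that the model and the chi-square test can both be read as tests of the dose effect, and neither is ranked first. In a non-blinded trial, that leaves room to report whichever p-value is smaller.

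**Working it through.** **Inputs from the documents.** Lower-dose rate 20%. A 50% increase, read as relative, gives 30% (marginal OR = (0.30/0.70)/(0.20/0.80) = 1.71). Dropout 20%; 350 per arm, 700 in total.

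**Assumed, because not stated.** Two-sided alpha 5%, power 80%, and the prognostic strength of the covariates.

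**Step 1: the plan's own figure.** With unpooled variance, n = (1.960 + 0.842)² × (0.20×0.80 + 0.30×0.70) / 0.10² = 290.4, so 291 per arm; 291 × 1.2 = 349.2, which rounds up to 350. The pooled-variance formula gives 294, and 294 × 1.2 = 353. So 350 is consistent with an unadjusted comparison of two proportions. (Dividing by 0.8 instead of multiplying by 1.2 gives 364 to 368.)

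**Step 2: power of the chi-square test.** Power = Φ[(0.10√n − 1.960√(2×0.25×0.75)) / √0.37]. This is 86.5% with all 350 per arm and 78.2% with 350 × 0.8 = 280 per arm. The two cases bracket full follow-up and complete loss of the expected dropouts.

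**Step 3: power with adjustment.** Simulation used 20,000 trials per cell, marginal rates of 20% and 30%, and three correlated baseline covariates. It compared the chi-square test with the Wald test of arm from the adjusted logistic model. Strength is the SD of the baseline log-odds. Monte Carlo standard error is 0.2 to 0.3 points.

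| SD (AUC) | 350/arm: chi-square | adjusted | change | 280/arm: chi-square | adjusted | change |
|---|---|---|---|---|---|---|
| 0 (0.50) | 86.5% | 86.3% | -0.2 | 78.2% | 78.0% | -0.2 |
| 0.25 (0.57) | 86.9% | 87.1% | +0.2 | 78.5% | 78.5% | 0.0 |
| 0.5 (0.63) | 86.2% | 87.6% | +1.4 | 78.7% | 80.1% | +1.4 |
| 0.75 (0.69) | 86.5% | 89.2% | +2.7 | 78.5% | 82.0% | +3.5 |
| 1.0 (0.74) | 86.7% | 91.3% | +4.6 | 78.6% | 84.4% | +5.8 |

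An independent simulation with a single baseline score gave the same picture. With 280 per arm it found 78.7% against 80.6% at AUC 0.64, and 78.6% against 84.3% at AUC 0.74.

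**Step 4: the gain in women.** With 350 per arm, the SD of the risk difference (unadjusted against standardised) was 0.0327 against 0.0320, 0.0325 against 0.0311, and 0.0327 against 0.0302 at strengths 0.5, 0.75 and 1.0. The variance reduction, 1 − (standardised/unadjusted)², is about 4%, 8% and 15%. The equivalent number of extra women, 700 × [(unadjusted/standardised)² − 1], is about 30, 65 and 120.

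**Step 5: type I error at 20% in both arms.** Chi-square 4.7-5.1%, adjusted 4.7-5.2%. Taking the smaller p-value gives 5.2, 5.5, 5.8, 6.3 and 6.7% with 350 per arm, and 5.4, 5.4, 5.6, 6.2 and 7.0% with 280 per arm, in order of increasing strength.

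**Step 6: robustness.**
- *Centre.* With an assumed centre SD of 0.3 and 3 or 10 centres, fixed and random centre effects differed by at most 0.4 points of power; type I error was 4.6-5.7%.
- *Missing covariates.* With AMH missing in 20% of women and AFC in another 20%, mean imputation cost at most 0.2 points; type I error was 4.5-5.2%.
- *Conditional OR.* Holding the marginal OR at 1.71, the conditional OR is 1.72, 1.76, 1.81 and 1.88 at strengths 0.25, 0.5, 0.75 and 1.0.

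**The case against.** The best reply is that this is an option, not a defect. An unadjusted intention-to-treat comparison of two proportions, sized as such, is coherent and keeps its type I error. That stands, and the point is put as one of efficiency.

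The gain may also be very small. Selection on low AMH or AFC may narrow the spread of two of the three covariates, which gives weight to the weaker rows of the table. At strength 0.25 the change is within simulation error, and at 0.5 it is 1.4 points. This also stands: the larger gains are possible, not shown.

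The chi-square could be a Wald or likelihood-ratio statistic from the model, since an OR comes from a logistic model too. The wording does not exclude this, and the match of 350 to an unadjusted formula does not settle it, because a trial with an adjusted analysis can be sized that way. On that reading, however, the covariates still have to be named and post-randomisation variables still have to be barred.

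Finally, the model may be meant for dose as received, since each arm has two regimens and daily and total dose are recorded. The two analyses would then not be rival tests of one hypothesis. That weakens the secondary point about choosing between p-values, but one sentence stating each analysis's role would still be needed to make it clear.

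**Conclusion.** The concern holds as a modest, inexpensive improvement. On its plain reading the plan judges significance with an unadjusted test and leaves three recorded baseline covariates unused. Under 20% against 30% and two-sided 5%, adjustment loses about 0.2 points of power if the covariates are uninformative. At strengths 0.5 to 1.0 it gains about 1.4 to 4.6 points with 350 per arm and 1.4 to 5.8 with 280 per arm. In the 280-per-arm case the chi-square has about 78% power, and adjustment at strength 0.5 or more brings it to 80% or above.

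The size rests wholly on the assumed prognostic strength. The conclusion that adjustment costs almost nothing and may help does not depend on which strength is true. Ranking the analyses matters less, but it removes a possible inflation of the type I error to between 5.2% and 7.0%.

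**What to change.** Name as primary the planned logistic model for cumulative pregnancy per randomised woman, with assigned arm as a two-level factor by intention to treat, adjusted for baseline age, AMH and AFC as continuous variables. State that no post-randomisation variable (such as day-6 estradiol, oocyte number or embryo counts) enters the model. Its test of arm gives the trial's p-value. Report the adjusted OR together with a standardised risk difference, and keep the chi-square test with its unadjusted OR as a sensitivity analysis. Include centre as a fixed or random effect according to the number of centres, which the documents do not give. Settle all of this before any comparison by arm, including the interim analysis after 350 women.

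The cost for age, AMH and AFC is wording only. Three smaller items follow:
- Centre is not on the data list and has to come from site records.
- Eligibility can be met on AMH or AFC alone, so one may be missing in some women; the plan should specify simple mean imputation.
- The adjusted OR is conditional and will lie somewhat further from 1 than the crude OR, which is why the standardised risk difference should accompany it.

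If the sponsor prefers to keep the chi-square test as primary, one sentence saying that it is an unadjusted test and that the model is secondary settles the ranking but forgoes the possible gain in power.
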